1. PURPOSE OF THE STUDY

a. Brief Summary

The purpose of the study is to determine if there are differences in the final height or hormone profile of patients placed on different forms of aromatase inhibitor now routinely used to increase stature; namely, Anastrozole and Letrozole. It also should determine if there are differences in the side effect profiles of the two drugs to be used. **Objectives**

We hope to learn if there are differences in effects of different forms of aromatase inhibitors on growth. There have been 3 randomized controlled trials using aromatase inhibitors to improve stature in a variety of circumstances (delayed puberty, idiopathic short stature, growth hormone deficiency), but no actual comparative trials between the different forms. We hope to elucidate if there are differences in the growth rates/final heights between the different forms of therapy. This will certainly add to the current, somewhat small literature about the use of these drugs, although they are widely used. We also will look at the differences between the side effect profiles of the two medications. **Rationale for Research in Humans**

Since we are looking at final adult heights, human subjects are necessary.

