2. STUDY PROCEDURES

a. Procedures

Patients from our endocrinology practice meeting our inclusion criteria will be consented into the study. They will be randomized into 1 of 2 treatment arms (Anastrozole 1 mg qday or Letrozole 2.5mg qday). Labs (gonadotropins, androgens, estrogens, growth factors, lipid profile) will be done every 6 months, bone age annually, and DEXA scans every 2 years.

We will see the patients annually until near final height (< 2 cm growth velocity per year), re-consenting in those over 18 years old. We will perform physical exams, obtain

anthropometric data, and repeat the above blood tests at least once off medication and perform imaging studies as warranted.

Beginning with this March 2016 renewal, we will no longer randomize to A vs L but use only A, continuing to collect observational data. **Procedure Risks**

We will be using the standard doses for the two drugs used. We will be monitoring with every 6 month physical exams and laboratory evaluation for possible side effects. At the discretion of the investigator, the medication may be reduced or discontinued, specifically if growth velocity falls below normal. **Use of Deception in the Study**

No deception will be used. Use of Audio and Video Recordings

No audio or video recording will occur. Alternative Procedures or Courses of Treatment

There are no alternatives to the above treatment. The only alternative would be to not start on the medication. Growth hormone is a theoretical option but is not standard of care for patients meeting these inclusion criteria. No standard treatment will be withheld. Will it be possible to continue the more (most) appropriate therapy for the participant(s) after the conclusion of the study?

Yes

g. Study Endpoint(s)

Our end point is final height which is defined as less than 2 cm of growth per year. We anticipate that all patients will reach this end point. **BACKGROUND**

a. Past Experimental and/or Clinical Findings

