We will be monitoring for arthralgia with the clinical history every 6 months. We will also collect laboratory data every six months: lipids, insulin levels, as well as estrogen and testosterone, gonadotropin and growth hormone levels. We will perform DEXA scans at baseline and two years into study to assess for decreases in bone density. Access to the labs/scans are all password protected.

d. Study Conclusion

The endpoint is final height. We will terminate when the growth rate has decreased to less than 2 cm per year. Since we will be monitoring clinical and performing physical exams every 6 months, if any of the side effects have been clinically significant, we will treat accordingly and/or terminate the use of the therapy.

e. Data Safety Monitoring Plan (DSMC)

i. Data and/or events subject to review

We will be monitoring, through laboratory evaluation, lipids, insulin sensitivity, gonadotropins, sex steroids, and growth hormone levels. We will monitor for changes in bone density through DEXA scans. Person(s) responsible for Data and Safety Monitoring

Protocol Director Frequency of DSMB meetings

All labs/scans will be monitored as soon as theyhave been received from the reference lab. Specific triggers or stopping rules

Physician's clinical assessment based on laboratory evaluation. DSMB Reporting

As needed

vi. Will the Protocol Director be the only monitoring entity? (Y/N)

Yes

vii. Will a board, committee, or safety monitor be responsible for study monitoring? (Y/N)

No

f. Risks to Special Populations

Short-term studies of aromatase inhibitors in this age group have not shown any significant risks, but there is a theoretical risk of issues with bone density, testicular function, and alterations to lipids/carbohydrate metabolism that is present. We will be monitoring for these risks during the course of the study. The direct benefit is increased ultimate height. We will be discussing these theoretical risks with the family in depth and will be obtaining assent from the subjects themselves. **BENEFITS**

Greater final height for the individual participant and possibly improved treatment options for future patients.

9. **PRIVACY AND CONFIDENTIALITY**

All participant information and specimens are handled in compliance with the Health Insurance Portability and Accountability Act (HIPAA) and privacy policies of Stanford University, Stanford Health Care, and Stanford Children's Health.

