Randomization to Letrozole vs. Anastrozole in Short Pubertal Males

NCT02137538

June 24, 2021

[name], Principal Investigator [name], Principal Investigator Stanford University Stanford, California 94305

Statistical Methods

Baseline auxologic and hormonal measures were summarized by treatment arm. Laboratory measures over time were presented as means with standard deviation, with key measures (total testosterone, estradiol, IGF-1) additionally displayed as boxplots by arm. Growth velocity (cm/year), height (cm), bone age (months), predicted adult height (cm), and DEXA z-scores over time were similarly visualized. Adverse events were listed by arm, and spinal film was assessed qualitatively.

To include all patients in an intent-to-treat approach, mixed effects linear regression was used to model each outcome as a function of treatment arm, indicators for follow-up timepoints, and their interaction for assessing effect modification of annual change by arm. Within-patient correlation was accounted for by a random effect. Estimated change since baseline with 95% confidence intervals were presented by arm if effect modification was deemed significant at the 0.05 alpha level and as an overall effect otherwise. All analyses were performed in the R statistical computing framework, version 4.0¹.

¹ R Core Team (2020). R: A language and environment for statistical computing. R Foundation for Statistical Computing, Vienna, Austria. URL https://www.R-project.org/

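### The SAP puts at least 8 outcomes through an unadjusted 0.05 interaction test and does not carry the Protocol's end point, final height, forward as primary

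*SAP*

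**What the plan says.** The Protocol's Brief Summary (1a) sets out to find "differences in the final height or hormone profile of patients" on the two aromatase inhibitors. Its end point section (2g) is narrower: "Our end point is final height which is defined as less than 2 cm of growth per year". Section 7d (Study Conclusion) again gives final height as the end point. No other end point is named.

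The SAP is one page, dated June 24, 2021, and written in the past tense. It says that "mixed effects linear regression was used to model each outcome as a function of treatment arm, indicators for follow-up timepoints, and their interaction". Change since baseline is then shown "by arm if effect modification was deemed significant at the 0.05 alpha level and as an overall effect otherwise".

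The outcomes that the SAP names fall into two groups:

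- Laboratory: "key measures (total testosterone, estradiol, IGF-1) additionally displayed as boxplots by arm". The other laboratory measures are not listed.
- Growth and bone: "Growth velocity (cm/year), height (cm), bone age (months), predicted adult height (cm), and DEXA z-scores over time were similarly visualized".

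The SAP designates no primary outcome, gives no order among outcomes and mentions no multiplicity adjustment. Height and predicted adult height appear over time, but final height does not appear.

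**The concern.** One rule at 0.05 is applied separately to every outcome. It does two jobs: it tests whether the drugs differ, and it chooses what the reader is shown.

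- **False by-arm findings.** With many outcomes and no adjustment, the chance that at least one crosses 0.05 without a real difference is well above 5%. Outcomes shown by arm are also selected for being significant, so their apparent differences tend to be too large.
- **Hidden comparisons.** An outcome that misses 0.05 is shown only as a pooled change. The reader then gets no estimate of the drug difference and cannot tell a small difference from an imprecise one. Yet comparing the drugs is the purpose of the study.
- **A lost anchor.** The Protocol's one end point would limit the first problem if the SAP made it primary. The SAP does not, and a document written in the past tense in 2021 cannot itself show which outcome was ranked first in advance.

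**Working it through.** The documents give no family-wise error rate, so there is no figure of theirs to reproduce.

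**Inputs**

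- Level per test: 0.05, unadjusted (SAP).
- Outcomes named in the SAP: 3 laboratory (total testosterone, estradiol, IGF-1) + 5 growth and bone (growth velocity, height, bone age, predicted adult height, DEXA z-scores counted once) = 8.
- Further laboratory outcomes: the Protocol lists classes in 2a ("Labs (gonadotropins, androgens, estrogens, growth factors, lipid profile) will be done every 6 months") and, in 7c, "lipids, insulin levels, as well as estrogen and testosterone, gonadotropin and growth hormone levels". I assume that gonadotropins means LH and FSH and that the lipid profile gives four results. Then 8 + 2 + 4 + 1 (insulin) = 15, and growth hormone makes 16. Counting lipids once and leaving out growth hormone gives 8 + 2 + 1 + 1 = 12.
- Correlation between test statistics: not in the documents. I assume values from 0 to 0.7.

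**Formula, independent tests, no true difference on any outcome**

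P(at least one false by-arm finding) = 1 − 0.95^k

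- k = 8: 1 − 0.95^8 = 33.7%
- k = 12: 1 − 0.95^12 = 46.0%
- k = 15: 1 − 0.95^15 = 53.7%
- k = 16: 1 − 0.95^16 = 56.0%

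The expected number of false findings is 0.05 × k: 0.4 for 8 outcomes and 0.8 for 16, whatever the correlation.

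**Correlated tests**

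These come from simulating two-sided z tests with equal correlation (200,000 draws). A z test stands in for the joint interaction test, so the figures are approximate.

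| Outcomes | Correlation 0.3 | 0.5 | 0.7 |
|---|---|---|---|
| 8 | 29.9% | 25.0% | 19.1% |
| 12 | 39.7% | 31.8% | 23.2% |
| 15 | 45.8% | 36.2% | 25.8% |
| 16 | 47.4% | 37.3% | 26.4% |

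Equal correlation across growth, bone, hormones and lipids is severe. If the 15 outcomes correlate only within blocks (4 growth, 1 DEXA, 5 hormones, 1 insulin, 4 lipids), the rate is 51.5%, 47.7% and 42.0% at within-block correlations of 0.3, 0.5 and 0.7.

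**If some outcomes truly differ**

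Only the outcomes with no true difference count. If the three named hormones did differ, the other five SAP outcomes would give 1 − 0.95^5 = 22.6% when independent.

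**If the interaction is judged timepoint by timepoint**

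The SAP does not say whether the interaction is one joint test or several. With three follow-up timepoints correlated 0.5 (assumed), the error per outcome rises to about 12.6%. Over 8 independent outcomes that gives 1 − (1 − 0.1259)^8 = 65.9%.

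**The case against.** The strongest reply is that this is a small comparative study with no stated confirmatory claim. The 0.05 rule decides how change is displayed, and nothing says that one significant outcome settles the study question. The *or* in the Brief Summary is summary prose and not a decision rule. Adjusting safety laboratory values would be partly a matter of taste. The Protocol also expects a real difference: section 7a regards excessive slowing of growth as more likely on letrozole, so a by-arm result for growth velocity or hormones may be true.

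Much of this stands, and it rules out three stronger readings that a reader might infer:

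- *A false finding is close to a coin toss.* That needs about 15 outcomes that are nearly independent or correlated only in blocks. The SAP names 8, and those overlap: growth velocity is change in height, and predicted adult height is derived from bone age (Protocol 6h).
- *The trial has no primary outcome.* The SAP has none, but the Protocol names a single end point twice. The gap lies between the two documents.
- *The three key laboratory measures form a key secondary tier.* The SAP sets them apart only for display as boxplots.

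The reply does not remove the problem. A display rule driven by significance still selects which outcomes are shown as differing by drug and suppresses the comparison for the rest. Neither document corrects this.

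**Conclusion.** The concern holds in limited form. Every outcome faces the same unadjusted 0.05 interaction test, that test decides between by-arm and pooled reporting, and the Protocol's end point has no place in the SAP.

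If no outcome truly differed, the chance of at least one false by-arm finding would be roughly 25% (8 outcomes, correlation 0.5) to 56% (16 independent outcomes). This rests on three assumptions: the number of outcomes modelled beyond the 8 named, the correlations, and one joint test per outcome. Correlation above 0.5 would take it below 25% (19% for 8 outcomes at 0.7), and separate timepoint tests would raise it. The rate covers only outcomes without a true drug difference. It does not mean that any particular by-arm result is false.

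The loss of the drug comparison for non-significant outcomes depends on none of these assumptions. It follows directly from the reporting rule.

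**What to change.** 1. Name the between-drug comparison of final height, as defined in Protocol 2g, as the single primary comparison at two-sided 0.05, and write that analysis into the SAP. With one designated test, its error is 0.05.
2. Report every other outcome, including testosterone, estradiol and IGF-1, as a secondary or exploratory between-drug estimate with a 95% confidence interval, whatever the interaction p-value and without a significance claim. If claims on the three named hormones are wanted, a Holm adjustment across them is an option. Bonferroni over all outcomes is a poorer choice: it would need 0.05/8 = 0.00625 per test for the 8 named outcomes.
3. List the outcomes modelled, and say whether the interaction is one joint test.
4. State that the order was taken from the Protocol after data collection.

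The cost is one added analysis and some SAP and report wording. The added analysis depends on follow-up that the Protocol (6m) expects to average 6–7 years from the start of treatment. Fewer outcomes can be called significant, and an order set after data collection gives only limited error control, even though its source is the Protocol.
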